6.6. Study Week 12 (Day 85)

The Study Week 12 visit must occur within ± 2 days of the scheduled date. During this visit, the following study procedures will be performed:

- A physical examination including body weight;
- Vital signs (temperature, sitting blood pressure, heart rate) after at least 3 minutes of rest;
- Blood samples will be collected for serum chemistry, hematology, serum pregnancy test (in women of childbearing potential), and PK measurements; the date and time of collection of the PK sample will be recorded;
- Biomarker plasma sample will be collected;
- A 12-lead ECG will be taken to exclude any clinically significant findings;
- The date and time of the last dose of study drug prior to collection of the PK sample will be recorded;
- If the subject has not yet taken the morning dose of study drug for this day, the subject will be asked to take the dose;

- A urine sample will be collected for urinalysis;
- The anatomic location and number of HS inflammatory nodules, abscesses, fistulae, and hypertrophic scars will be recorded;
- Follow-up photography of lesions will be completed;
- Compliance with daily recording of pain in diaries will be checked and re-training provided, if necessary;
- Items for the Sartorius and modified Sartorius scores will be collected;
- IHS4 score will be calculated;
- The Investigator will complete the HS-PGA;
- Study personnel will record health-economic information;
- Subjects will be asked to complete the SF-36 v2, EQ-5D-5L, HiSQOL, DLQI, and WPAI:SHP forms;
- Drug accountability will be performed; the returned bottles of study drug will be checked to make sure the subject is taking the study drug as instructed;
- Study drug will be dispensed. Note: At this visit, subjects who were assigned to placebo arm will be re-randomized to receive 10 mg or 30 mg avacopan twice a day;
- Any changes in concomitant medication use will be recorded, including alcohol intake, recreational drug use, non-prescription medications, herbal preparations or special diets;
- Any adverse events will be recorded;
- After all study procedures have been completed, the subject will be reminded to:
 - Record severity of skin pain and study drug dosing in daily diary;
 - Come to the study center for the Week 16 study visit;
 - Store the study drug in a cool and dry place according to label instructions for the duration of the study;

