6.7. Study Week 16 (Day 113)

The Study Week 16 visit must occur within ± 2 days of the scheduled date. During this visit, the following study procedures will be performed:

- A physical examination including body weight;
- Vital signs (temperature, sitting blood pressure, heart rate) after at least 3 minutes of rest;

- Blood samples will be collected for serum chemistry, hematology, serum pregnancy test (in women of childbearing potential), and PK measurements; the date and time of collection of the PK sample will be recorded;
- The date and time of the last dose of study drug prior to collection of the PK sample will be recorded;
- If the subject has not yet taken the morning dose of study drug for this day, the subject will be asked to take the dose;
- A urine sample will be collected for urinalysis;
- The anatomic location and number of HS inflammatory nodules, abscesses, fistulae, and hypertrophic scars will be recorded;
- Follow-up photography of lesions will be completed;
- Compliance with daily recording of pain and study drug dosing in diaries will be checked and re-training provided, if necessary;
- Items for the Sartorius and modified Sartorius scores will be collected;
- IHS4 score will be calculated;
- The Investigator will complete the HS-PGA;
- Study personnel will record health-economic information;
- Subjects will be asked to complete the SF-36 v2, EQ-5D-5L, HiSQOL, DLQI, and WPAI:SHP forms;
- The study site personnel will make sure the subject is taking the study drug as instructed;
- Any changes in concomitant medication use will be recorded, including alcohol intake, recreational drug use, non-prescription medications, herbal preparations or special diets;
- Any adverse events will be recorded;
- After all study procedures have been completed, the subject will be reminded to:
 - Record severity of skin pain and study drug dosing in daily diary;
 - Come to the study center for the Week 20 study visit;
 - Store the study drug in a cool and dry place according to label instructions for the duration of the study;
 - Take the study drug as instructed. On study visit days, it is preferable that the subjects take the morning dose of study drug at the site following the collection of PK samples, if applicable to that visit; and
 - Continue taking all their other concomitant medications as usual.

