Subjects will be asked to take 3 capsules of study drug orally with water and preferably with food every morning, and 3 capsules with water and preferably with food in the evening approximately 12 hours after the morning dose, as instructed. Study drug will be taken for 36 weeks (252 days) continuously.

VI. General Analytical Considerations

A. Baseline and Study Day

Baseline

Baseline for analysis purposes is defined as the last assessment prior to treatment start date/time.

For Subject's Global Assessment of Skin Pain (Numerical Rating Scale, Skin Pain NRS), the average of the last 7 assessments prior to the date of first dose of study drug will be used as Baseline. If there are only 3 to 6 daily assessments available, the average of the available assessments will be used. If there are 2 or less assessments available, the subject's Baseline will be considered as missing.

Change from Baseline

Change from baseline is defined as the post baseline value minus the baseline value. Percent change from baseline is calculated as follows: Percent change = (Change from baseline / Baseline) * 100.

Reduction from Baseline

Reduction from baseline is defined as the baseline value minus the post baseline value. Percent reduction from baseline is calculated as follows: Percent reduction = (Reduction from baseline / Baseline) * 100.

Study Day

Study day for analysis purposes is defined as (date of event – treatment start date) (+ 1 if the event occurs after treatment start date).

B. Analysis Visit Window

All visits including scheduled, unscheduled and early termination visits will be assigned to analysis visits using analysis visit windows based on the actual date the assessment took place. The start day of the analysis window will be calculated as the midpoint between the scheduled assessment and previously scheduled assessment for that parameter. The end day of the analysis window will be calculated as the midpoint between the scheduled assessment and the next scheduled assessment for that parameter. Where multiple measurements for a particular parameter appear within an analysis window, the scheduled visit will be used. If no scheduled visit appears in the analysis window, the result closest to the target day will be used. If equidistant and both are unscheduled and/or early termination visits, the later result will be used for the summary measure.

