Though all measures may not be used in data summaries (e.g., two lab measures within the same analysis visit window), all measurements appear in the datasets and listings. For subjects where the event date is missing, the study day and analysis window will also be missing. See Tables 1-3 below for the analysis windows.

Table 1 Mapping for Endpoints Measured at Study Day 1, Weeks 2, 4, 8, 12, 16, 20, 24, 28, 32, 36, and 44

Scheduled Visit	Target Study Day	Visit Window (Study Day)			
Period 1: Study Day = visit date - date of first dose of study drug in Per 1 +1					
Baseline	1	≤1			
Week 2	15	2 to 22			
Week 4	29	23 to 43			
Week 8	57	44 to 71			
Week 12	85	72 to min (114, the study day of the randomization date for Period 2)			

Period 2: Study Day = visit date - date of first dose of study drug in Period 2 +1						
Entry of Period 2	1	≤1				
Week 16	29	2 to 43				
Week 20	Yeek 20 57 44 to 71					
Week 24	85	72 to 99				

Scheduled Visit	Target Study Day	Visit Window (Study Day)
Week 28	113	100 to 127
Week 32	141	128 to 155
Week 36	169	156 to 183
Week 44	197	≥ 184

Table 2 Mapping for Skin Pain NRS

Scheduled Visit	Target Study Day	Visit Window (Study Day)							
Period 1: Study Day = 1+1	Period 1: Study Day = visit date - date of first dose of study drug in Period 1+1								
Baseline	-1	<1							
Week 2	14	1 to 21							
Week 4	28	22 to 42							
Week 8	56	43 to 70							
Week 12	84	71 to min (113, the study day of the randomization date for Period 2 -1)							
Period 2: Study Day = 2 +1	visit date - date of first	dose of study drug in Period							
Entry of Period 2	-1	<1							
Week 16	28	1 to 42							
Week 20	56	43 to 70							
Week 24	84	71 to 98							
Week 28	112	99 to 126							
Week 32	140	127 to 154							
Week 36	168	155 to 182							
Week 44	196	≥ 183							

Table 3 Mapping for Endpoints Measured at Study Day 1, Weeks 4, 12, 16, 28, 36, and 44

Scheduled Visit	Target Study Day	Visit Window (Study Day)						
Period 1: Study Day = visit date - date of first dose of study drug in Period 1 +1								
Baseline	1	≤1						
Week 4	29	2 to 43						
Week 12	85	44 to min (114, the study day of the randomization date for Period 2)						
Period 2: Study Day	Period 2: Study Day = visit date - date of first dose of study drug in Period 2							
+1	T	Γ						
Entry of Period 2	1	≤1						
Week 16	29	2 to 43						
Week 28	113	44 to 155						
Week 36	169	156 to 197						
Week 44	225	≥ 198						

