The number and percentage of subjects who had taken prior/concomitant medications will be summarized by therapeutic class and preferred term, and by treatment group. Subjects taking the same medication multiple times will only be counted once for that therapeutic class and preferred term. A subject level listing will also be presented.

Study Drug Exposure and Compliance

Study drug exposure will be determined using the morning/evening drug diary, study drug dispensing and return records. The study drug exposure including duration, total dose, average daily dose and compliance will be summarized for Period 1 and Period 2 separately for the safety population. Individual subject data listings will also be provided. If date of last dose is not available, the date of discontinuation from study will be used.

The following are the definitions of the drug exposure measures:

- Duration of Study Drug: Defined as Last Dose Date First Dose Date +1.
- Total Dose: Defined as total dose of Avacopan taken in mg.
- Average Daily Dose (mg/day): Defined as [total dose of avacopan taken (mg) / treatment duration (days)].
- Percent compliance

Duration on treatment will be calculated using the last dose date – first dose date + 1. The first dose date in Period 1 and the last dose date in Period 2 will be collected from EDC, the last dose date in Period 1 and the first dose date in Period 2 will be determined from the drug accountability form (DA). If the last dose date in Period 1 is missing for subjects with early termination, then the date of last visit will be used as the last dose date in Period 1. For subjects who did not return data on DA, the date of last dose and compliance will be calculated based on subjects' daily dosing diary.

VIII. Efficacy Analyses

All efficacy analyses will be performed using the ITT population unless otherwise noted. All statistical testing will be two-sided, with the Type I error rate at $\alpha = 0.05$. Summary tables will be presented for the Period 1 and Period 2 separately. The stratification factor values as collected in the electronic case report forms will be used for all stratified efficacy analyses, and subgroup analyses.

A. Timing of Analyses

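### The Week 12 analysis window runs to Day 114 against the SAP's own midpoint rule (Day 99), and its only earlier cut-off is a date the documents describe for placebo subjects alone

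*SAP*

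**What the plan says.** SAP VI.B states one rule for all windows: "The end day of the analysis window will be calculated as the midpoint between the scheduled assessment and the next scheduled assessment for that parameter". Its tables then give the Week 12 row as follows.

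- Table 1 (lesion counts, so HiSCR): "72 to min (114, the study day of the randomization date for Period 2").
- Table 2 (skin pain NRS): "71 to min (113, the study day of the randomization date for Period 2 -1").
- Table 3 (endpoints with fewer visits): Day 44 to the same limit as Table 1.

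The protocol places Week 12 at Day 85 and Week 16 at Day 113 (sections 6.6 and 6.7), each within 2 days. On who is randomised at Week 12, Protocol 6.6 says "subjects who were assigned to placebo arm will be re-randomized to receive 10 mg or 30 mg avacopan twice a day". Protocol 3 and 3.2, the schedule footnote in both documents and SAP IV.A agree, and Protocol 3.2 has the avacopan groups simply continue their regimen.

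In all three tables the Period 2 clock starts at the first Period 2 dose. SAP VII.C derives that date without limiting it to any arm: "the first dose date in Period 2 will be determined from the drug accountability form (DA"). A missing Week 12 HiSCR counts as non-response (SAP VIII.D).

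**The concern.** There are two problems. First, the printed upper limit does not follow from the stated rule and takes in the target day of the next visit. Second, the only thing that shortens the window is an event documented in one arm. Read literally, a placebo subject's window closes at re-randomisation, while an avacopan subject's stays open to Day 114.

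Suppose a subject starts Period 2 drug without a Week 12 lesion count. On placebo the subject is a non-responder. On avacopan a count from Week 16, or from an unscheduled visit, falls inside the printed Week 12 window. An arm-dependent rule for data entering the primary endpoint is undesirable whatever its size, and this one leans towards avacopan.

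**Working it through.** **Midpoint rule against the tables.** Window end = (target day + next target day)/2.

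| Table | Row | Calculation | Rule gives | Printed |
|---|---|---|---|---|
| 1 | Week 2 | (15 + 29)/2 | 22 | 22 |
| 1 | Week 4 | (29 + 57)/2 | 43 | 43 |
| 1 | Week 8 | (57 + 85)/2 | 71 | 71 |
| 1 | Week 12 | (85 + 113)/2 | **99** | **114** |
| 2 | Week 12 | (84 + 112)/2 | **98** | **113** |
| 3 | Week 12 | (85 + 113)/2 | **99** | **114** |

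In Table 1 the rule also reproduces every Period 2 upper limit from the table's own targets (43, 71, 99, 127, 155, 183). Week 24, whose Period 2 target is also Day 85, is printed as 72 to 99. Table 3 is weaker evidence of a slip because it leaves the rule elsewhere too: its Week 4 window ends at 43, where (29 + 85)/2 = 57.

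Day 114 is 114 − 99 = 15 days past the midpoint and one day past the Week 16 target. Week 16 visits are allowed on Days 111–115, so those on Days 111–114 fall inside.

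**Window by arm, Period 2 entry on Day 85 (Table 1).**

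- Placebo: 72 to min(114, 85) = Days 72–85, 14 days.
- Avacopan, if no Period 2 randomisation date exists: Days 72–114, 43 days.

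For the avacopan subject, Period 2 day = study day − 84. The Week 16 window (Period 2 Days 2–43) therefore covers study Days 86–127. Days 86–114 belong to both windows, and no rule says which takes the result.

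**Who is affected for HiSCR.**

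- On-time Week 12 count present: it is the scheduled visit and closest to target, so it is used in every arm.
- Late Week 12 visit up to Day 114: the placebo limit is the re-randomisation day itself, inclusive, so the count is kept in every arm.
- Never enters Period 2: Day 114 applies in every arm.
- Dropped out: generally no later count to borrow.
- Starts Period 2 drug without a count and has one later, by Day 114: the only group treated differently.

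**Size for HiSCR.** From SAP IV.C: 30% response, n = 130 per arm, two-sided α = 0.05. Assumed, because the documents give no figure: a share m of each arm is in that last group; its later counts respond at 30%; there is no true effect. Then p(avacopan) = 0.30, p(placebo) = 0.30(1 − m), and the spurious difference is d = 0.30m. The test is approximated by an unstratified pooled z:

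P(reject) = 1 − Φ[(1.96·se0 − d)/se1] + Φ[(−1.96·se0 − d)/se1],

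where se0 is the pooled and se1 the unpooled standard error.

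For m = 5%: d = 0.015, se0 = √(2 × 0.2925 × 0.7075/130) = 0.0564, se1 = √[(0.285 × 0.715 + 0.30 × 0.70)/130] = 0.0564. P = 0.045 + 0.013 = 0.058.

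| m | Spurious difference | Type I error, normal approximation |
|---|---|---|
| 0 | 0 | 5.00% |
| 1% | 0.3 points | 5.03% |
| 2% | 0.6 points | 5.13% |
| 5% | 1.5 points | 5.81% |

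Exact binomial enumeration gives 5.04% at m = 0, 5.06% at 1% and 5.15% at 2%.

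**NRS30.** SAP VIII.B averages the 7 diary days in the window closest to the target, Day 84. With Period 2 entry on Day 85 and complete diaries:

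- Placebo, window 71 to 85 − 1 = 84: Days 78–84.
- Avacopan, window 71–113: Days 81–87 (84 ± 3), three of them in Period 2.

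No missing data are needed here. Changing 113 to 98 alone would not cure it, because Days 85–87 would still lie inside the avacopan window.

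**The case against.** A reader might infer that the plan directs Week 16 data into the primary endpoint for avacopan only, and so carries a material bias. The documents do not support that, for four reasons.

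- **The date is undefined, not shown to be absent.** Table 1 names no arm. The schedule places randomisation at Week 12 in a common column, although its footnote concerns placebo. Sites are blinded and treatment-specific kits go to every subject at that visit, so a system transaction for everyone is plausible. If its date is what the tables mean, the asymmetry disappears. The documents do not say.
- **Other text points against using the later count.** SAP II describes Period 1 as ending at Week 12, SAP VIII.D tests Period 1 data, and SAP VI.C confines LOCF to the period. This argues for excluding a Week 16 count. It does not settle the matter: the tables do the mapping, they do not enforce the restriction, and they are silent on precedence.
- **The affected group is a sliver.** Counting, re-randomisation and dispensing share one visit. Attrition over the whole trial is put at about 7%, and dropouts mostly have no later count, so shares of 5–10% have no support in the documents. The SAP's COVID-19 sensitivity analysis (SAP IX.I) sets altered or missing Week 12 assessments to non-response in all arms, which covers one likely route but leaves the primary analysis unchanged.
- **Day 114 may be deliberate.** 114 = 85 + 29 and 113 = 84 + 29, which looks like an end-of-period allowance. If so, the text should say so.

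What stands is the contradiction between rule and tables, the undefined cut-off, the overlapping days, and the NRS30 difference.

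**Conclusion.** The SAP should be corrected, but this is not a demonstrated bias in the primary result. It is certain that the Week 12 limits in Tables 1–3 contradict the midpoint rule and pass the Week 16 target. It is conditional, on no Period 2 randomisation date being recorded for avacopan subjects, that the window differs by arm.

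Under that condition the HiSCR effect is small and favours avacopan: 0.3–0.6 points and a type I error of about 5.1% if 1–2% of subjects are affected. The 5% case (1.5 points, 5.8%) is a stress test. For NRS30, second in the ranked secondary endpoints, the averaged days differ by arm as written even with full data. I put no size on that, because the documents give no pain course over time.

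**What to change.** For every arm, define the end of the Week 12 window as the earlier of:

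- the midpoint: Day 99 in Tables 1 and 3, Day 98 in Table 2; and
- the first Period 2 dose: the pre-dose assessment on that day in Tables 1 and 3, and the day before it in Table 2, matching the existing minus one.

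Replace the Period 2 randomisation date with the first Period 2 dose date, which the SAP already derives. State that no assessment after that dose can serve as Week 12, which also removes the overlap with Week 16. If a longer allowance is intended for subjects who have not started Period 2, write it as an explicit exception that applies to all arms.

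The cost is three table cells and a sentence or two. SAP I requires changes to the primary analysis before the Week 12 database freeze. Under the midpoint limit a few very late Week 12 visits become non-response, in all arms alike.

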Data collected at all visits will be included in the data listings with visit presented as reported by the site.

C. Missing Data

Imputation for Efficacy variables:

The approaches listed below will be used for handling missing data:

- Non-responder imputation (NRI): Subjects who have missing data at the time point of interest are treated as though they did not respond to the treatment.
- Last Observation Carried Forward (LOCF): The LOCF analyses will use
 the last observed non-missing evaluation (last completed non-missing
 evaluation, from composite endpoint) from the previous visit within the
 particular period for efficacy measures assessed to impute missing data at
 later visits in the same period. Baseline efficacy evaluations will not be

carried forward. LOCF will be the primary approach in the analysis of continuous variable.

- Observed case (OC): Missing data are not imputed. Only subjects with available data at the given time point are considered.
- Multiple Imputation (MI) Markov Chain Monte Carlo (MCMC) imputation: Using multiple imputation methodology, missing data in Period 1 are imputed based on the MCMC method, please see Section VIII D for details

The following table depicts which missing data handling approaches should be used based on variable priority (primary, secondary, other) and variable type (binary, continuous).

		Missing Data Handling Approach					
Endpoints	Variable Type	NRI	MI	LOCF	ос		
Primary Efficacy	Binary	P	SEN	SEN			
Primary Efficacy (COVID-19)	Binary	P		SEN			
Secondary/ Other Efficacy	Binary	P	SEN				
(selected ones only, see Page 47)	Continuous			P1	SEN		

P=Primary method, SEN=Sensitivity method

Imputation for AE and Concomitant Medication Start Dates:

For analyses of AEs and concomitant medication usage, a complete date must be established in order to correctly identify the AE or medication as occurring during treatment or not. For purposes of imputing missing components of partially-reported start and stop dates for AEs and for medication use, the algorithms listed below will be followed. Start and stop dates of AEs or concomitant medication will be displayed as reported in the subject data listings (i.e., no imputed values will be displayed in data listings).

Partial AE and concomitant medication start dates will be imputed as follows:

- If year is missing, no imputation will be performed.

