- If both day and month of the start date are missing, the day and month will be imputed with the day and month of the first study dose date if the year is equal to the year of first dose. Otherwise, the month and day is imputed as the first day of the year (01 Jan).

¹⁼For selected endpoints

 If only day is missing, and if the year and month are equal to the first dose date, the day will be imputed as day of the first dose date. Otherwise, the day will be imputed as "01".

D. Multiple Study Centers

No adjustment for stratification by the study centers is planned. However, centers will be grouped by geographic region and a subgroup analysis will be conducted to determine if region impacts the primary endpoint.

E. Covariate Adjustment in Primary Analysis

Continuous variables of the secondary/other efficacy endpoints, change from Baseline to Week 12 in the Sartorius score, modified Sartorius score, IHS4 score, HS-PGA, inflammatory and non-inflammatory nodule count, abscess count, draining, non-draining and total fistula count, total AN count, SF-36 v2 (domains and component scores) and EQ-5D-5L (visual analogue scale and index), HiSQOL, DLQI, and WPAI:SHP will be analyzed using a mixed effects model for repeated measures. This model will include treatment group, visit, treatment-by-visit interaction, and randomization strata (Hurley Stage II or Hurley Stage III, anti-TNF drug use or anti-TNF drug naive) as factors, and corresponding baseline as covariate.

Change from Baseline to Week 12 in WPAI:SHP will be analyzed using an ANCOVA model which includes treatment group, randomization strata (Hurley Stage II or Hurley Stage III, anti-TNF drug use or anti-TNF drug naive) as factors, and corresponding baseline as covariate.

F. Sample Size Reassessment

No sample size reassessment is planned.

G. Interim Analyses or Timing of Analyses

No interim analyses planned.

H. Test Sizes

All confidence intervals will be two-sided with 95% coverage.

I. Multiple Comparisons/Multiplicity

For the primary efficacy endpoint testing, the avacopan 30 mg vs. placebo in HiSCR (H_{11}) and the avacopan 10 mg vs. placebo in HiSCR (H_{12}), a hierarchical procedure will be used to control the overall α at 0.05 level.

That is if H_{11} is rejected at a 2-sided alpha level of 0.05, then the H_{12} will be tested at 2-sided alpha level of 0.05.

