For the analysis of time to loss of response (LOR), the treatment difference between the avacopan 30 mg vs. placebo to avacopan 30 mg, avacopan 10 mg vs. placebo to avacopan 10 mg, avacopan 30 mg group vs. avacopan 10 mg group, and placebo to avacopan 30 mg vs. placebo to avacopan 10 mg will be analyzed using the stratified log-rank test with the baseline Hurley Stage (Stage II vs. III), concomitant antibiotic therapy with allowed antibiotics (Yes vs. No), and anti-TNF drug use (Treatment naïve vs. Previous treatment) as the stratification variables. Subjects without LOR or lost follow-up will be censored at the date of the last assessment of number of HS lesions. Kaplan-Meier curves will be provided by treatment group.

IX. Safety Analyses

Safety analyses will be performed in the Safety Analysis Set using the actual treatment group.

A. Adverse Events

All subjects will be assessed regularly for potential occurrence of adverse events (AEs) throughout the study until the subject is off study. The Medical Dictionary for Regulatory Activities (MedDRA; Version 21.1) will be used to code all adverse events to a System Organ Class (SOC) and Preferred Term (PT).

A treatment-emergent AE (TEAE) in Period 1 is defined as any AE that occurs after the first dose of study treatment in Period 1 and before the date of first dose of study treatment in Period 2.

A treatment-emergent AE (TEAE) in Period 2 is defined as any AE that occurs after the first dose of study treatment in Period 2.

A treatment-emergent AE (TEAE) for all avacopan, is defined as any AE that occurs after the first dose of avacopan treatment in study.

The incidence of TEAEs will be summarized and tabulated by treatment group and period.

The severity of each AE will be assessed as mild, moderate, severe, lifethreatening, fatal, or death. Several occurrences of the same AE in one subject will be counted once and the one with maximum severity will be counted.

The relationship of each AE to the blind study medication will be classified as probably not related or possibly related. Several occurrences of the same AE in one subject will be counted once and the one with the maximum relationship to blind study medication will be counted. If an AE is missing the relationship to blind study medication, the event will be assumed to be probably related for analysis and summarization.

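### Partial AE start dates are imputed against the first study dose only, so most missing-day events that truly begin after the Period 2 switch, in the switch month, are counted in Period 1

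*SAP*

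**What the plan says.** SAP VI.C (Imputation for AE and Concomitant Medication Start Dates) gives the aim of its date rules as having a complete date "in order to correctly identify the AE or medication as occurring during treatment or not". The rules for start dates are:

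- **Day missing:** "if the year and month are equal to the first dose date, the day will be imputed as day of the first dose date". For every other month, "Otherwise, the day will be imputed as" 01.
- **Day and month missing:** they are "imputed with the day and month of the first study dose date if the year is equal to the year of first dose"; in any other year the date becomes 1 January.
- **Year missing:** no imputation.

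There is no branch for the first Period 2 dose.

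SAP IX.A then needs more than an on-treatment flag. A Period 1 TEAE is one with onset "after the first dose of study treatment in Period 1 and before the date of first dose of study treatment in Period 2". The definition that follows reads: "A treatment-emergent AE (TEAE) in Period 2 is defined as any AE that occurs after the first dose of study treatment in Period 2". An all-avacopan TEAE is "any AE that occurs after the first dose of avacopan treatment in study". The main incidence table attributes each event to the treatment being taken in the period when it began.

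Under SAP IV.A, placebo subjects who complete Period 1 are re-randomized to one of the two avacopan doses. SAP VII.C already derives the first Period 2 dose date, from the drug accountability form. The protocol has no rule for partial AE dates, and the change table in SAP X does not add one.

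**The concern.** The trial has two treatment starts, but the imputation rule recognizes only the first. At Day 1 the rule resolves doubt towards treatment: an event in the month of first dose with no recorded day is placed on the dose date. At Week 12 it resolves doubt towards Period 1.

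For a subject coming from placebo, that second boundary separates placebo from avacopan. An event that began on avacopan can then be counted as a placebo event and drop out of both the Period 2 and the all-avacopan summaries. Safety against placebo is a primary objective, and the all-avacopan table is meant to hold everything seen after first exposure.

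**Working it through.** The plan states no figure here, so the date rule is applied to the TEAE cuts.

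**Inputs**
- Period 1 lasts 84 days (Protocol 3.3), so the first Period 2 dose is nominally at Day 1 + 84 days.
- The imputation rule is from SAP VI.C and the cuts are from SAP IX.A.
- Planned size is about 130 per arm, 390 in total (SAP IV.C).
- Assumption: within the month in which Period 2 starts, dose day and true onset day are independent and uniform.

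**Which branch applies.** Two dates 84 days apart cannot share a calendar month (0 of 1,464 consecutive start dates tried). In the switch month the first-dose branch therefore never applies, and the day is always set to 01. Months wholly inside one period are not affected.

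**30-day month, 30 × 30 = 900 equally likely pairs of dose day and onset day**
- Onset on or after the dose (truly Period 2): 30 + 29 + … + 1 = 465; 465/900 = 0.517.
- Of these, the dose is on the 1st in 30 pairs, and the imputed date is then not before the dose. Sent to Period 1: 465 − 30 = 435.
- Share of true Period 2 events misplaced: 435/465 = 0.935.
- Share of all missing-day events in that month misplaced: 435/900 = 0.483.
- True Period 1 events moved to Period 2: 0, because the imputed 1st is never later than the true onset.

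**Real calendar, 1,464 start dates.** The Period 2 dose falls on the 1st in 3.3% of cases, 93.6% of true Period 2 events are misplaced, and these are 48.3% of all missing-day events in the month. The two calculations agree.

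**Example.** A placebo subject has Day 1 on 23 September 2019 and the first Period 2 dose on 16 December 2019. An AE truly begins on 20 December but is recorded as December 2019. It is imputed to 1 December, counted as a Period 1 placebo TEAE, and left out of the Period 2 and all-avacopan counts.

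**Year only known.** With Day 1 spread evenly over a calendar year and onset uniform from Day 85, about 77% of true Period 2 events through Day 252 go to Period 1, or about 69% if onset runs through Day 308.

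**Who can be given the wrong treatment.** Only placebo subjects who enter Period 2: at most 130 of 390, or 33.3%, before Period 1 dropout and the exclusion of Site 138 (SAP VI.J).

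**The case against.** A reader might infer that the rule inflates the placebo column and so tilts the placebo-controlled safety comparison in favor of avacopan. The documents do not support that. The same rule applies in all three arms, so missing-day events in the switch month are also drawn back into Period 1 for subjects on avacopan from Day 1, raising those columns too. With similar rates of partial dates, the inflation would be about equal. The direction of any net shift is not known.

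Other points carry weight:

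- **Rarity.** The percentages are conditional on a missing day in one calendar month. AEs are recorded at Week 12 and again about four weeks later (Protocol 6.6 and 6.7), missing data are queried with sites (Protocol 10.1.8), SAEs are reported within 24 hours (Protocol 7.2.4), and the laboratory-defined events of special interest come from dated samples. The most important events are the least likely to have partial dates.
- **Visibility.** Listings show dates as reported, so affected events can be found.
- **Wording.** The day-missing rule does not name a period. Day 1 is the natural reading, since the companion rule refers to the first study dose and SAP VII.C names the period when it means one, but this is an inference.

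These points limit the size and the reach of the problem. They do not remove the mismatch: the rule's aim is an on-treatment flag, and the tables use its output to assign a period and a treatment.

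**Conclusion.** The concern holds in this limited form. As written, the rule puts about 94% of true Period 2 events with a missing day in the switch month into Period 1, and the error runs one way. The firm consequences are wrong-treatment attribution for placebo subjects who entered Period 2, and loss of those events from the Period 2 and all-avacopan tables. A bias in the Period 1 comparison between arms is not shown.

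The figures rest on uniform onset within the month, on a Period 2 dose 84 days after Day 1, and on reading the anchor as the first Period 1 dose. The number of partial dates is not in the documents, so the absolute effect is unknown and probably small. It still merits correction, because a stated rule gives a wrong result and the date needed to repair it is already derived.

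**What to change.** In SAP VI.C:

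- State that the existing anchor is the first Period 1 dose.
- Add, for AEs and in all arms alike: if the known month and year equal those of the first Period 2 dose, impute that dose date unless the stop date or other recorded information shows an earlier onset.

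In SAP IX.A, define Period 2 and all-avacopan TEAEs as starting on or after the relevant first dose date. At present an onset on the day of the first Period 2 dose is excluded from Period 1 and not clearly included in Period 2, so the new imputation could lose the events it is meant to recover.

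Two extensions should be avoided:

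- A year-only rule for placebo-to-avacopan subjects alone would make imputation depend on arm and deplete the placebo column by construction.
- The concomitant-medication rule should stay as it is where it decides Week 12 non-response (SAP VIII.C and VIII.D). Dating a disallowed treatment to the 1st is the cautious choice there; moving it to the first Period 2 dose could leave a Week 12 response standing that should not.

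The cost is a few sentences and a small programming change. Misclassification is redirected, not removed: without stop-date or other evidence, true Period 1 events with a missing day in that month (435/900, about 48% of partial-date events there) move to Period 2, while true Period 2 events charged to Period 1 fall from 94% to none. That is the direction the SAP already takes at Day 1.
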